5.8 Poolability Analyses

All investigational sites will follow the requirements of a common protocol and standardized data collection procedures and forms. The primary efficacy and safety endpoints will be presented separately for each site using descriptive statistics. Poolability of the primary efficacy endpoint across investigational sites will be evaluated using a logistic regression model with a fixed effect for site. If there is a significant effect of site (using a significance level of 0.15), the analysis will be repeated using

S	tatistical Analysis Plan	Pa	ge 22 of 25
Sponsor	Study		Version
Neuspera	Clinical Study of Neuspera's Implantable Sacral Nerve Stimulation (SNS) System in Patients with Symptoms of Urinary Urgency Incontinence (UUI)		17.0

site as a random effect. Sites enrolling fewer than 5 subjects will be removed from these poolability analyses.

Additional exploratory analyses may be performed to understand any variations in outcome by site. Assessment of poolability by geography (US vs. OUS) will be performed based on logistic regression.

5.9 Safety Analyses

Investigators are required to report all AEs during the course of the study. Investigators are responsible for providing a description of all AEs, including the date of the event, treatment and the clinical outcomes for the subject. Investigators will evaluate each event for seriousness, severity and relatedness to the procedure, device or stimulation therapy. All adverse events, including unanticipated adverse device effects (UADE), and serious adverse events (SAE) will be reported for all enrolled subjects.

For Phase I, all adverse events reported over the course of the study will be summarized for all enrolled subjects. Any adverse events reported for consented subjects who were not enrolled will be reported separately.

For Phase II, all adverse events reported over the course of the study will be summarized for the mITT analysis set. Any adverse events reported for enrolled (i.e., consented) subjects who are excluded from mITT analysis set will be reported separately.

Adverse events will be tabulated with the number of events and subjects with event for each event type and overall. Rates will be reported as the number of subjects who experience at least one event during the analysis interval out of the total number of subjects with follow-up to the beginning of the analysis interval. Serious adverse events will also be tabulated. The rate of all AEs and SAEs reported in the study will be reported.

All AEs and SAEs will also be summarized by relatedness. Adverse events leading to death or study discontinuation will be provided in a listing format.

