# 5.3 Study Duration

The enrollment period is expected to take approximately 12 months for Phase II. The total expected duration of the clinical trial is dependent on the length of time to regulatory approval. Implanted subjects from Phase I and Phase II will continue to be followed until US PMA approval. Health Canada approval, European approval, CE Mark, may be achieved earlier or later than PMA approval. If achieved earlier, all Canadian and EU subjects will continue to be followed in the trial until US PMA approval is achieved which is estimated to be up to 36 months or longer for some subjects. Subjects enrolled earlier will have a longer follow-up than subjects enrolled later. In Phase II, subjects enrolled later may be followed for less than 36 months but at least until the 12-month follow-up visit is completed. It is estimated that the first subjects enrolled in Phase II will be in the study approximately 3 years. If Neuspera determines regulatory approval will not be achieved, the study will be closed.

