#### 7.5.8.11 Post-Explant 30-Day Follow-up

A 30-day follow-up visit is required for all subjects where the implant procedure was attempted but the device was not implanted or where the device was explanted. The following measures are required:

- Vitals signs
- Changes to medication (including OAB medications) and OAB therapies
- Adverse event assessment
- Wound check

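### SAP 5.9 adverse event rates ignore time observed within the interval, so whole-study and late-interval proportions can understate long-term risk; add exposure-adjusted rates and cumulative incidence.

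*SAP*

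**What the plan says.** SAP 5.9 sets one rule for the adverse event and serious adverse event tables. The numerator is given by "Rates will be reported as the number of subjects who experience at least one event during the analysis interval" and the denominator by "out of the total number of subjects with follow-up to the beginning of the analysis interval". For Phase II the summary covers the whole study: "all adverse events reported over the course of the study will be summarized for the mITT analysis set". Event counts are shown as well: "Adverse events will be tabulated with the number of events and subjects with event for each event type and overall". The section lists no analysis intervals. Neither document plans subject-time rates, Kaplan-Meier estimates or any other allowance for censoring of adverse events. A full adverse event summary over study participation is a listed secondary endpoint (Protocol 6.1.5, SAP 5.6.3).

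Follow-up is unequal by design:

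- Protocol 5.3 says that "subjects enrolled later may be followed for less than 36 months but at least until the 12-month follow-up visit is completed". It expects the first Phase II subjects to stay about 3 years, and "The enrollment period is expected to take approximately 12 months for Phase II".
- Protocol 7.5.8.11 says that "A 30-day follow-up visit is required for all subjects where the implant procedure was attempted but the device was not implanted", and Protocol 2.6 has these subjects exit after 30 days. They remain in the mITT set.
- Protocol 7.4.4 has implanted subjects who leave explanted and then followed for 30 days before exit.

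**The concern.** An event can be seen only until a subject exits or the data are cut. In the whole-study table, a subject seen for one month after a failed attempt and a subject seen for 36 months each add one to the denominator. In an interval that starts at Month 12, a subject cut off soon after Month 12 counts as if observed to the end.

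Read as the risk to a patient who keeps a chronic implant for three years, such a proportion is too low. The shortfall depends on accrual speed and approval date rather than on the device, so it also moves from one data cut to the next. This matters for any later safety update; SAP 5.10 commits to supplying further follow-up safety data at the 100-day meeting.

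**Working it through.** **The plan's own figures.** SAP 5.9 states a rule and no number for its effect. The interim percentages in Protocol 3.1.2.2 are plain crude proportions and reproduce as such: 33/70 = 47.1%, 11/70 = 15.7%, 36/39 = 92.3%.

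**Inputs from the documents.** Follow-up is at least 12 and about 36 months at most. A 12-month accrual with a 36-month maximum implies about 24–36 months. Implant success is assumed to be 95%, so 5% are failed attempts seen for about one month. Twelve explants are reported with 130 attempted implants (Protocol 3.1.2.2.2), without their timing.

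**Assumptions not in the documents.** Follow-up C is uniform on 12–36 or 24–36 months. Cumulative hazard is H(t) = c·t^k, with k = 1 (constant) or k = 0.5 (front-loaded). Exits are none or 10% a year. The 36-month risk is 2% to 50%. Subjects who leave are taken to stay at the same risk.

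**Formula.** For an interval from s to 36 months:

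- reported proportion = E[1 − exp(−(H(C) − H(s))) | C > s]
- full-interval risk = 1 − exp(−(H(36) − H(s)))
- understatement = 1 − reported/full

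**Rare events, no exits (checkable by hand).**

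- Constant hazard, whole study: mean C is 24 or 30 months, so 1 − 24/36 = 33% or 1 − 30/36 = 17%.
- Constant hazard, Months 12–36: 1 − 12/24 = 50% or 1 − 18/24 = 25%.
- Front-loaded, whole study: mean √C is 4.845 (12–36) or 5.468 (24–36), so 1 − 4.845/6 = 19% or 1 − 5.468/6 = 9%.
- Front-loaded, Months 12–36, with √12 = 3.464: 1 − (4.845 − 3.464)/(6 − 3.464) = 46% or 1 − (5.468 − 3.464)/2.536 = 21%.

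**Full grid.** The low end of each range is a 36-month risk of 50%, the high end 2%.

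| Follow-up (months) | Hazard | Exits per year | Whole study | Months 12–36 |
|---|---|---|---|---|
| 12–36 | constant | none | 27.1–33.1% | 46.2–49.9% |
| 12–36 | constant | 10% | 34.1–40.2% | 49.5–53.2% |
| 24–36 | constant | none | 12.5–16.5% | 21.3–24.9% |
| 24–36 | constant | 10% | 22.2–26.7% | 27.0–30.7% |
| 12–36 | front-loaded | none | 14.7–19.1% | 43.1–45.5% |
| 12–36 | front-loaded | 10% | 19.6–24.6% | 46.4–48.8% |
| 24–36 | front-loaded | none | 6.4–8.8% | 18.8–20.9% |
| 24–36 | front-loaded | 10% | 12.9–16.2% | 24.3–26.5% |

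**Exits built from the documents' counts.** Take 5% seen for 1 month and 12/130 = 9.2% explanted evenly over year 1 and seen 30 days longer (mean 7 months). The remaining 85.8% are seen for a mean of 24 months. Mean observed time is 0.05 × 1 + 0.092 × 7 + 0.858 × 24 = 21.3 months. For a rare event with constant hazard the understatement is 1 − 21.3/36 = 41%. At a 36-month risk of 15% it is 39.5%, so 15% would be reported as 0.605 × 15% = 9.1%.

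**Early tables.** Exits at 10% a year give λ = −ln(0.9)/12 = 0.00878 per month. The share of time observed is (1 − e^(−λT))/(λT): 0.974 at 6 months and 0.949 at 12, a loss of about 3% and 5%. Failed attempts would add at most 0.05 × 5/6 = 4 points at Month 6 and 0.05 × 11/12 = 5 points at Month 12, and only for events that do not need a device in place.

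**Very common events.** At a 36-month risk of 95%, constant hazard and no exits, the whole-study figure falls to 4–12%.

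**The case against.** The strongest reply is that the crude proportion is a correct statement of how many subjects had an observed event. The tables are descriptive, with no hypothesis test. Event counts are also tabulated, and SAP section 7 provides listings. The filing is planned at six months (SAP 5.6.3.1), before staggered late follow-up matters much. All of this stands, and it is why n/N should be kept. It does not turn the proportion into a long-term risk, and event counts without observed time give no rate.

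Three stronger readings are tempting, and the documents do not support them.

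- A reader might infer that long-term rates are understated by a fixed quarter to a half. The stated 12-month accrual implies 24–36 months of follow-up. Without exits the whole-study figure is then 12–17% under constant hazard and 6–9% if events are front-loaded. Front-loading is plausible: Protocol Table 4 includes implant site pain, vomiting and respiratory failure, and the one Phase II serious event was judged possibly related to the procedure.
- A reader might infer that the SAP plans a Month 12–36 table. It names no such interval, so that case is illustrative. Requiring follow-up to the interval's start also removes failed attempts and earlier explants from later intervals.
- A reader might link this rule to the protocol's remark that fractures, migrations and revisions compare well with commercial devices. That is an interim narrative in Protocol 3.1.2.2.2 and 4.4, not an output of SAP 5.9. The stopping rule in SAP section 8 has its own numerator and denominator.

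A further objection is sound: plain Kaplan-Meier would treat explant as ignorable censoring. Explanted and never-implanted subjects carry no device. In Phase I, eleven of twelve explants followed unsatisfactory therapy or device performance. For device-related events the grid rows without exits are therefore the better guide, and the remedy must handle explant as a competing event.

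**Conclusion.** The point holds as a structural one. SAP 5.9 ignores time observed within the interval while follow-up ranges from about 1 to about 36 months. Whole-study and late-interval proportions therefore run low when read as long-term risk. For 36-month risks of 2% to 50%, the understatement is roughly 6–41% for the whole study and 19–53% for a Month 12–36 interval. These figures rest on assumed follow-up distributions, exit rates and hazard shapes; none is stated in the documents, and very common events fall below the range. The 6- and 12-month tables lose about 3–5% to exits at an assumed 10% a year. No hypothesis, sample size or success criterion is affected. This is a cheap improvement to a stated rule, not an error in the primary analysis.

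**What to change.** In SAP 5.9:

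1. Keep n/N as a description and state the analysis intervals.
2. For whole-study and post-Month-12 tables, add events, and subjects with a first event, per 100 subject-years observed, from implant or attempt to exit or data cut.
3. For the same tables, add cumulative incidence of first event at 6, 12, 24 and 36 months with numbers at risk. For device-related events, treat permanent explant and death as competing events, and start device-event time only in implanted subjects.
4. Use items 2 and 3, not the crude proportion, for any statement about long-term risk.

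Event onset, implant, explant and exit are already recorded, so no new data are needed. The cost is SAP wording and a few more table columns, and late rates will look less favourable.

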5.10 Interim Analyses

The sponsor will use Phase I, feasibility phase, of the trial to assess system performance, subject compliance and determination of the daily stimulation duration for Phase II. Phase I data will also be examined as needed to determine if modifications need to be made to training of the centers on implant technique, subject instructions, duration of stimulation, etc. Formal statistical conclusions from Phase I will not be made so there are not type I error concerns.

S	tatistical Analysis Plan	Pa	ge 23 of 25
Sponsor	Study		Version
Neuspera	Clinical Study of Neuspera's Implantable Sacral Nerve Stimulation (SNS) System in Patients with Symptoms of Urinary Urgency Incontinence (UUI)		17.0

For Phase II, there are no planned interim analyses for the purpose of adaptive study modifications or early stopping for success. An interim analysis will be performed when the 60th Phase II subject has completed the 3-month post implant visit. For this interim analysis, the primary and secondary safety and effectiveness endpoints will be assessed, but at the three-month timepoint. This interim analysis will be used for business purposes only, no modifications to the study will be made based on this analysis, and outcomes will not be published or shared with investigators, patients, or Neuspera employees with direct subject access.

In order to ensure that adequate safety information is available to the agency, the sponsor commits both to completing the study to the original planned sample size of 120 attempted implants and to submitting updated information with additional follow-up safety data at the time of the 100-day meeting. Operational bias will be minimized by having a third party, independent statistician separate from study operational personnel and study statistician, who will perform the interim analysis.

5.11 Protocol Deviations and Device Deficiencies

Deviations from the procedures outlined in the protocol will be reported by investigational sites on case report forms. Protocol deviations will be summarized for all deviations and by type with event counts and number of subjects with at least one deviation.

Device deficiencies will be summarized in a similar fashion to protocol deviations.

6 Changes from Planned Analyses

Any changes to planned statistical analyses determined necessary prior to performing the analyses will be documented in an amended Statistical Analysis Plan and approved prior to the analysis when possible. Any other deviations or changes from the planned analyses deemed necessary due to violation of critical underlying statistical assumptions, data characteristics, or missing data will be clearly described in the clinical study report with justification and rationale.

7 Subject Listings

Subject listings will be provided for the primary endpoints. Listings will also be provided for adverse events.

8 Stopping Rules for Phase II

Phase II will use stopping rules designed to suspend enrollment and trigger a series of events if at any time there is sufficient statistical evidence to conclude that any of the Phase II probabilities of device

s	tatistical Analysis Plan	Pa	ge 24 of 25
Sponsor	Study		Version
Neuspera	Neuspera Clinical Study of Neuspera's Implantable Sacral Nerve Stimulation (SNS) System in Patients with Symptoms of Urinary Urgency Incontinence (UUI)		17.0

fracture, device dislodgement/migration, or surgical revision exceed comparator probabilities from an approved device. The comparator probabilities are shown in Table 2.

Table 2. Comparator event probabilities guiding the Phase II stopping rule. Values shown are point estimates (upper limits of 95% confidence intervals).

Event Type	Proportion of
Event Type	Subjects with Event
Fractures	0.014 (0.022)1
Dislodgements/Migrations	0.026 (0.036)2
Surgical Revisions	0.118 (0.239) ³

Phase II will use the following stopping rules. At each occurrence of device fracture, dislodgement/migration, or surgical revision, form an exact one-sided binomial confidence interval for the event probability. Determine whether any of the following conditions is met:

- The lower limit of the interval for device fractures exceeds 0.014.
- The lower limit of the interval for device dislodgements/migrations exceeds 0.026.
- The lower limit of the interval for surgical revisions exceeds 0.118.

The numerator for each event is the number of subjects who have experienced the event up to that time. The denominator will be the number of subjects implanted up to that time. For device fractures and migrations/dislodgements, the confidence level of the interval will be 95%. For surgical revisions, the confidence level will be 80% if 50 or fewer subjects have been implanted; if more than 50 subjects have been implanted, the confidence level will be 95%. If any of the above conditions is met, the following actions will be taken:

- Both enrollment and implants will be suspended and FDA will be notified within 7 days
- Neuspera will conduct a root cause analysis to determine the cause of the safety events that triggered the stopping rule
- Neuspera will prepare a safety report for submission to the DSMB

¹ Based on Medtronic's ²020 Product Performance Report showing 19 subjects experienced lead fractures out of 1,314 subjects followed (page 167).

² Based on Medtronic's 2020 Product Performance Report showing 34 subjects experienced lead dislodgements/migrations out of 1,314 subjects followed (page 167).

³ Based on Medtronic Clinical Summary Report stating 6 out of 51 subjects had "surgical procedures to resolve adverse events or technical observations, or due to lack of efficacy ... from the time of test lead implant to 6-month follow-up after full system implant" (page 16).

Statistical Analysis Plan		Pa	Page 25 of 25	
Sponsor	Study		Version	
Neuspera	Clinical Study of Neuspera's Implantable Sacral Nerve Stimulation (SNS) System in Patients with Symptoms of Urinary Urgency Incontinence (UUI)		17.0	

- The DSMB will convene, review the safety report and root cause analysis, and make a
 recommendation on study continuance (continue enrollment post FDA review and approval,
 continue enrollment suspension pending FDA decision and/or further investigation by the
 sponsor, etc.)
- Neuspera will submit to FDA the safety report, the root cause analysis, and the DSMB's recommendation
- FDA will make final determination on study continuance

The stopping rules will take effect only when more than 15 subjects have been implanted. After more than 15 subjects have been implanted, all events, including any events within the first 15 subjects, will be counted in assessing the criteria for stopping. However, if there are 4 or more surgical revisions when 15 or fewer subjects have been implanted, the stopping rule is triggered.

